## Overview:

[figure not shown]
This will be a randomized, single site, pilot clinical trial. Assuming a potential drop-out rate of 20%, up to 24 subjects will be enrolled to achieve a goal of having at least 20 subjects (10 per group) complete the study, per protocol. Participants will be recruited from among patients who have been diagnosed with Stage 1 primary hypertension, based on blood pressures between 130-139 mmHg systolic, and/or 80-89 mmHg diastolic, as documented by their health care providers on two separate occasions during the prior 18 months. This, in the absence of known clinical cardiovascular disease, risk for cardiovascular disease of  $\geq$  10%, or other medical conditions associated with likelihood for development of hypertension, and who have not yet been started on pharmacological treatment.

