Those who have no other exclusions, are interested to participate, and provide informed consent will be randomly assigned to receive 8-16 sessions of in-office acoustic stimulation linked to brainwave activity (HCC), over a maximum of 4 weeks, while continuing their other current clinical care, or to continue their current clinical care alone (CCC). There will be pre- and post-intervention data collection to include systolic and diastolic BP, and many secondary outcome measures including measures of autonomic cardiovascular regulation (continuous recording of BP and HR for calculation of measure of HRV and BRS), behavioral symptom outcomes (ISI, PSQI, ESS, CES-D, GAD-7, PCL-C, PSS), quality of life measure (Quality of Life Scale, QOLS), short physical activity recall (International Physical Activity Questionnaire, IPAQ-SF), and function performance measures (drop stick reaction testing, and grip strength). All measures will be collected at an enrollment visit (V1), for both groups. Intervention will begin 0-14 days thereafter for the HCC group. BP and heart rate (HR) recording will be repeated prior to the start of the 7th session for the HCC group. Post-intervention data collections will include an immediate postintervention visit (V2, 1-14 days after intervention completion for HCC, 4-6 weeks after V1 visit for CCC), an intermediate post-intervention visit (V3, primary outcome, 4-6 weeks after intervention completion for HCC, and 8-10 weeks after V1 for CCC), and a final follow up visit (V4, 12-14 weeks following completion of the intervention for HCC, and 16-18 weeks after V1 for CCC). The primary outcome will be differential change in the systolic and diastolic BP from V1 to V3. Following V4, those in the CCC group will be offered the opportunity to receive a course of HCC, and those who accept will have up to 3 months to schedule a brainwave assessment 0-14 days before starting sessions and continue to be followed for data collections at 1-14 days (V5), 4-6 weeks (V6), and 12-14 weeks (V7) after completing their HIRREM sessions.

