## Number of HCC/CCC Sessions and Length of Study:

All baseline measures, along with a brainwave assessment, will be obtained during an enrollment visit (V1). The intervention will commence 0-14 days later. Participants will receive 8-16 in-office intervention sessions over a maximum of 4 weeks. HCC sessions will be about 1.5-2 hours in length. Participants may receive two intervention sessions during a half day period. All will receive a total of 6 sessions during the first three days of the intervention period. Participants will be encouraged to complete the remainder of the intervention sessions within two-three weeks, with a maximum of four weeks to complete the sessions. If received as two sessions per half day, subject involvement will thus require 4-8 half days during the intervention period. Following the initial 6 sessions, some sessions may be arranged as singles (one per day), if needed due to schedule issues.

In the HCC group, one to fourteen days after the final intervention session there will be a postintervention data collection visit (V2). V2 will be 4-6 weeks after V1 for the CCC group. All measures will be repeated at V2, but no brainwave assessment will be obtained. An intermediate post-intervention data collection visit, will occur at four to six weeks after completion of the intervention for the HCC group, and 8-10 weeks after V1 for the CCC group, with all measures repeated. Data collected at the V3 visit will comprise the primary outcome data for the study. A final data collection visit (V4) will occur 12-14 weeks after completion of the intervention for the HCC group, and 16-18 weeks after V1 for the CCC group, with repeat of the outcome measures and a brainwave assessment. At V4, official study involvement is complete for those in the HCC group, while those randomized to the CCC group will be offered an opportunity to be scheduled to receive a course of HCC. Those who accept will receive a course of in-office acoustic stimulation linked to brainwaves (brainwave assessment 0-14 days before starting sessions), as described for the HCC group, and will continue to be followed for data collections at 1-14 days (V5), 4-6 weeks (V6), and 12-14 weeks (V7), as done during the initial intervention period, after completing their HCC sessions. Participants will have up to 3 months to crossover.

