# Intervention Period:

During the intervention period, subjects will receive in-office sessions of acoustic stimulation linked to brainwave activity (HIRREM, HCC), while relaxing in a zero gravity chair. Sessions last about 1.5-2 hours, and two can be done in a half day, with a short break between sessions. All subjects must receive the initial 6 sessions, two per day, on three consecutive days. Thereafter, subjects are encouraged to complete all sessions within 7-14 days, and in no longer than 4 weeks, without going longer than 5 days between sessions. BP and HR recordings will also be repeated prior to the start of the 7th session. Those assigned to the CCC group will continue with their current clinical care, including any life-style, non-pharmacological therapies that they may be employing.

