# Post-Intervention Data Collection Visits:

For participants in the HCC group, between 1-14 days after completion of the intervention, participants will return for a post-intervention data collection visit (V2). Those in the CCC group will return at 4-6 weeks after V1. All measures will be repeated, but no brainwave assessment done. This visit will take about 45 minutes.

Between 4-6 weeks after completion of the intervention, participants in the HCC group will return for the primary outcome data collection visit (V3). This will occur at 8-10 weeks after V1 for those in the CCC group. All measures will be repeated, including a brainwave assessment. This visit will require about 120 minutes.

Between 12-14 weeks after completion of the intervention, participants in the HCC group will return for a final data collection visit (V4). The V4 visit will be between 16-18 weeks after V1 for those in the CCC group. All measures including a brainwave assessment will be repeated for a final time. This will complete the official study involvement for participants in the HCC group, while those in the CCC group will be offered an opportunity to be scheduled to receive a course of HCC, and this will be discussed. This visit will take about 120 minutes.

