The HIRREM process is individualized for each recipient, such that the specific protocols chosen, the session length, and the total number of sessions are variable. Technologists time sessions and choose protocols to facilitate an overall trend toward greater hemispheric symmetry and more optimal proportionation in frequency ranges, between and within cortical regions, based upon data from the initial assessment and the ensuing sessions (Gerdes et al., 2013). Each participant in the HCC group will receive at least 8 sessions. The final number of HIRREM sessions, which may be extended to as many as 16, will depend on continuous review of brain patterns relative to progress towards improved balance and quieting of electrical amplitudes, as well as progress and stability of self-reported status regarding symptoms such as sleep and stress.

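### The primary-outcome visit in HCC is dated from intervention completion, so HCC participants who never start have no V3 date and early stoppers have only an ambiguous one

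*Combined protocol and SAP*

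**What the plan says.** The Overview fixes the primary visit as "V3, primary outcome, 4-6 weeks after intervention completion for HCC, and 8-10 weeks after V1 for CCC". The neighbouring visits follow the same pattern: "V2, 1-14 days after intervention completion for HCC, 4-6 weeks after V1 visit for CCC", and "V4, 12-14 weeks following completion of the intervention for HCC, and 16-18 weeks after V1 for CCC". The Methods part of the Abstract, Number of HCC/CCC Sessions and Length of Study, and Post-Intervention Data Collection Visits repeat these anchors for V3 and V4.

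There is one variation. For V2 in HCC, Number of HCC/CCC Sessions and Length of Study says "one to fourteen days after the final intervention session there will be a postintervention data collection visit (V2"), which refers to the last session and not to completion.

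The course is 8 to 16 sessions in at most 4 weeks. HIRREM Sessions says "Each participant in the HCC group will receive at least 8 sessions", and Intervention Period says "All subjects must receive the initial 6 sessions, two per day, on three consecutive days". Neither section says what follows for visits if this is not met.

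Other Data Collection, Measures, and Process states that every participant is measured at V1 and at three later visits, but sets no dates. The Overview allows for 20% drop-out among up to 24 enrolled, to "achieve a goal of having at least 20 subjects (10 per group) complete the study, per protocol". Statistical Analysis makes the V1-to-V3 contrast from a linear mixed model the primary test. It names no analysis population and no rule for missing visits.

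**The concern.** A visit date that depends on finishing treatment can be calculated only for people who finish. In CCC the V3 window follows from V1 for everyone. In HCC, a coordinator who follows the text cannot calculate V3 for a non-starter and has to improvise for an early stopper.

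If some of these people are not seen at V3, the loss arises from the schedule, occurs in one arm only, and is tied to behaviour after randomisation. The primary contrast would then move towards HIRREM completers versus all controls. HIRREM Sessions ties the number of sessions to brain-pattern progress and self-reported symptoms, so a link between stopping and response is plausible, although the documents do not establish one.

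The mixed model helps only as far as it has data. Before the post-intervention visits, the only blood-pressure recording after V1 is the one before session 7. Someone who stops at 6 sessions or fewer and is not seen again contributes V1 alone, which tells the model nothing about that person's change. The Abstract says the pilot should supply effect-size estimates that might justify larger trials, so a distortion here would carry forward. A V3 reading that was never taken cannot be recovered later.

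**Working it through.** **1. The plan's own enrolment figure.** Inputs from the Overview: 20 completers, 20% drop-out, 24 enrolled. 20 × 1.20 = 24 reproduces the figure. Dividing instead gives 20 / 0.80 = 25. With 24 enrolled, 24 × 0.80 = 19.2 completers are expected, and 20 of 24 corresponds to a loss of 4/24 = 16.7%. This is drop-out from the study over both arms, not a rate of stopping sessions.

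**2. Which dates can be calculated.** Completion can be read strictly (a course of at least 8 sessions was finished) or loosely (sessions have ended, whatever their number).

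| Participant | V2 | V3 and V4, strict | V3 and V4, loose |
|---|---|---|---|
| CCC, anyone | from V1 | from V1 | from V1 |
| HCC, finished at least 8 | yes | yes | yes |
| HCC, stopped before 8 | yes, if dated from the last session | no date | from the last session |
| HCC, never started | no date | no date | no date |

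The non-starter has no date under either reading. The early stopper's V3 depends on a definition that the plan does not give.

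**3. Where the windows fall for HCC completers, in weeks after V1.** Earliest: start on day 0 and take 8 sessions at two per day, so the last session is on day 3. Latest: start on day 14 and take 28 days, so the last session is on day 42.

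- V2: (3 + 1)/7 = 0.6 to (42 + 14)/7 = 8.0; CCC 4-6.
- V3: 3/7 + 4 = 4.4 to 42/7 + 6 = 12.0; CCC 8-10.
- V4: 3/7 + 12 = 12.4 to 42/7 + 14 = 20.0; CCC 16-18.

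Each CCC window lies inside the span already open to HCC completers.

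**4. Illustrative size.** If a share d of HCC has no V3 and their mean change differs from the completers' by X, a completers-only HCC mean is off by d × X. The documents supply neither d nor X. Assume 12 in HCC, 1 to 2 without V3, and X of 5 to 10 mmHg:

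- lower end: 1/12 × 5 = 0.42 mmHg;
- upper end: 2/12 × 10 = 1.67 mmHg.

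**5. Scale.** The pilot tables under Specific Relevant Pilot Data give standard errors for systolic change of 5.5 (n = 10) and 1.91 (n = 18). The SDs are 5.5 × √10 = 17.4 and 1.91 × √18 = 8.1 mmHg. With 12 per arm, the standard error of the difference is SD × √(1/12 + 1/12), which is 3.3 to 7.1 mmHg. The pilot readings were supine and continuous, whereas the primary outcome is seated and oscillometric, so this is a rough scale only.

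**The case against.** The strongest reply is that the plan does intend to measure these people. A reader might infer from the windows that HCC non-completers have no primary-outcome visit. The documents do not support that. Other Data Collection, Measures, and Process provides three later visits for every participant, no section withdraws early stoppers from follow-up, and Participant Compensation pays by data-collection visit and not by session. This stands: what is missing is a date and a rule, not the intention.

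Second, completion as at least 8 sessions is an inference from HIRREM Sessions, which describes what participants will receive and sets no visit rule. On the loose reading an early stopper has dates for V2, V3 and V4. Even on the strict reading, V2 can be dated from the last session, so such a person may give the mixed model V1 and V2. This also stands, and it means the completers-only arithmetic is not the bias of the planned model. It does not help a non-starter, and it does not settle which reading site staff should use.

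Third, both pilots described in the protocol report no drop-outs. They were open-label series in other cohorts, and this plan itself allows for 20%.

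Fourth, dating some HCC visits from V1 puts two anchors in one arm. That is a real cost, but a limited one, because the borrowed windows fall within the range that completers already span.

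**Conclusion.** The point holds in a limited form. V3 and V4 in HCC depend on an event after randomisation. HCC non-starters have no date for either visit, and HCC participants who stop before 8 sessions have an ambiguous one. With a goal framed around per-protocol completers and no stated analysis population, following the schedule literally can remove primary data from one arm selectively.

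The size and direction of any bias are unknown. The 0.4 to 1.7 mmHg range rests wholly on assumed values for the number lost and for how they differ, and it applies to a completers-only mean. It is below even the smaller rough standard error of 3.3 mmHg.

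Two stronger inferences should be avoided. A reader might apply the 20% allowance to 12 HCC participants and treat the result as the expected number without V3. That allowance covers losses from both arms, and people who leave the study lack V3 under any anchor. The documents give no rate for those who stop sessions but would still attend. A reader might also conclude that the bias favours HIRREM. That requires stoppers to do worse than completers, which nothing in the documents shows.

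For a 24-person pilot this should be corrected before enrolment. It does not invalidate the design.

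**What to change.** In the Overview, Number of HCC/CCC Sessions and Length of Study, and Post-Intervention Data Collection Visits (and in the Abstract, to match), state that every randomised participant is invited to V2, V3 and V4 whatever number of sessions was received. For HCC participants who do not start or do not complete the course, date these visits with the existing CCC windows: 4-6, 8-10 and 16-18 weeks after V1. Say what counts as completing the course for the purpose of visit dating. In Statistical Analysis, include all of them as randomised in the primary V1-V3 contrast and report completers as a secondary analysis.

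The cost is the wording, a few visits that are already planned, two anchors within HCC, and possibly a smaller estimated effect than among completers. People who leave the study altogether will still lack V3. No treatment rule changes.

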#### Stage 1 Hypertension Study Flow Chart

CCC Group Who Complete V1-V4 and Choose to Receive a Course of HCC

## Participants/Subjects:

Participants will be recruited by physician referral and advertisement, from among adults ages 18 and older with a diagnosis of Stage 1 primary hypertension, and absence of clinical atherosclerotic cardiovascular disease, or a cardiovascular risk score of  $\geq$  10, placing them in the lower risk sub-group for Stage 1 hypertension. Stage 1 Hypertension will be defined by blood pressure readings between 130-139 mmHg systolic, and/or 80-89 mmHg diastolic, documented by their health care provider on two occasions, at two separate office visits, during the prior 18 months. A prior diagnosis of Stage 2 hypertension, the presence of known cardiovascular disease, or other conditions associated with development of hypertension such as renovascular disease, renal failure, pheochromocytoma, aldosteronism, are not present. Those who have been recently diagnosed, and who at their health care provider's recommendation, are attempting nonpharmacological or lifestyle modifications, will also be eligible. Cardiovascular risk will be calculated using the tool provided online by the American College of Cardiology (Cardiology, 2017). Those who also meet other inclusion/exclusion criteria, and are interested to participate in the study, will be offered participation. Each subject must be able to provide an informed consent. As part of the screening process, potential participants will need to provide documentation of having BP in the target range, and results from their most recent cholesterol testing (total cholesterol, HDL, and LDL).

Interested subjects will be informed with a more detailed description of the study, and the extent of their commitment, through phone calls or email communications. If no exclusions are apparent from initial phone or email communications, potential participants will complete an online eligibility screening form, which will be reviewed by the study team. If potential participants express continued interest in the project and have no major exclusions, and after receipt of BP and cholesterol testing documentation as noted above, the cardiovascular risk will be calculated. If confirmed that they have < 10 % risk for cardiovascular disease, they will be scheduled for an enrollment visit (V1) at which time an informed consent will be completed. As part of the informed consent process, study procedures, schedule for visits, and duration of participation will again be reviewed, and alternatives discussed, including the option to not enroll in this project, and follow up with their primary health care provider.

After informed consent is obtained, a blood pressure will be obtained to confirm eligibility. Those with BP less than 130 mmHg systolic or 80 mmHg diastolic, or systolic BP  $\geq$  140 mmHg systolic, or  $\geq$  90 mmHg diastolic, will be considered as screening failures, and will not move on to the remaining enrollment visit activities. For those confirmed to have an eligible baseline blood pressure reading, a brief medical history will be obtained, randomization will be completed, and baseline study measures obtained, prior to the start of the intervention, or continuation of current care. Those scheduled for an enrollment visit will also be provided a copy of Appendix B, Handout to Study Participants, and/or a welcome email with details. Prior to randomization, women of childbearing potential will also have a urine pregnancy test performed at the WFBH Outpatient Laboratory, 2nd floor, Piedmont Plaza 1 Building. If positive, they will be excluded from the study.

## Inclusion Criteria:

Adults,  $\geq$  18 years of age, diagnosed with Stage 1 primary hypertension, who have systolic BP ranging from 130-139 mmHg, or diastolic BP ranging from 80-89 mmHg, who under their medical provider's management are not on medical therapy, and who do not have known clinical cardiovascular disease or a cardiovascular risk score of  $\geq$  10%.

# Exclusion Criteria:

Unable, unwilling, or incompetent to provide informed consent

Physically unable to come to the study visits, or to sit comfortably in a chair for up to two hours at a time

Weight is over the chair limit (285 pounds)

Known atherosclerotic cardiovascular disease

Cardiovascular risk score of ≥ 10% (per http://tools.acc.org/ASCVD-Risk-Estimator-

Plus/#!/calculate/estimate/)

Prior diagnosis of stage 2 hypertension

Ongoing need for treatment of hypertension with medications

Known seizure disorder

Known or anticipated pregnancy

Severe hearing impairment (because the subject will be using headphones during the interventions Ongoing need for treatment with opiate, benzodiazepine, or anti-psychotic medications, anti-depressant medications such as SSRI, SNRI, or tricyclic, and sleep medications such as zolpidem or eszopiclone Anticipated and ongoing use of recreational drugs, alcohol, or energy drinks Ongoing need for treatment with thyroid medications Are enrolled in another research study that includes an active intervention Have previously received brainwave optimization (BWO), used a B2 or B2v2 wearable device, or previously participated in a HIRREM research study

Participants are encouraged to discuss their participation with their health care provider following completion of the study because HIRREM may alleviate some of the need for medications they were on previously. Participants are requested to abstain from using any alcohol or recreational drugs during the intervention, and for at least six weeks following sessions since use of these substances may cause reversal or cessation of the benefits of HIRREM. In addition, the participants are also advised to suspend chiropractic, cranial-sacral therapy, and bio-energy work during the intervention, and for at least six weeks following.

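### The alcohol and drug abstinence request is timed by the HIRREM sessions and covers every in-window HCC primary reading, with no stated CCC counterpart before V4

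*Combined protocol and SAP*

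**What the plan says.** The closing paragraph of the Exclusion Criteria makes two requests. The first concerns alcohol and drugs: "Participants are requested to abstain from using any alcohol or recreational drugs during the intervention, and for at least six weeks following sessions". Its reason is specific to the intervention: "since use of these substances may cause reversal or cessation of the benefits of HIRREM". The second concerns other therapies, where participants are "advised to suspend chiropractic, cranial-sacral therapy, and bio-energy work during the intervention, and for at least six weeks following". Neither names an arm, and neither gives a starting point other than the intervention or its sessions.

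The same section lists as an exclusion, for all candidates: "Anticipated and ongoing use of recreational drugs, alcohol, or energy drinks".

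Under Post-Intervention Data Collection Visits, the primary visit is set for the intervention arm as "Between 4-6 weeks after completion of the intervention, participants in the HCC group will return for the primary outcome data collection visit (V3". For the control arm: "This will occur at 8-10 weeks after V1 for those in the CCC group". CCC is offered a HIRREM course only after V4 (Overview).

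The Primary Objective is the effect of adding acoustic stimulation to current care, compared with current care alone. The Methods part of the Abstract has both groups continue their other care, non-pharmacological and lifestyle measures included. The Intervention Period section repeats this for CCC.

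**The concern.** An abstinence request whose clock starts with the sessions has no start date for a participant who has no sessions. Read literally, it reaches HCC throughout the period that matters for the primary outcome and never reaches CCC before V4. Drinking and drug use are behaviours that could bear on blood pressure. The plan accepts that kind of reasoning elsewhere: its Secondary Objectives collect physical activity so that between-group swings with a possible influence on blood pressure can be seen.

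At stake is what the primary contrast means. If only HCC is asked to abstain, the difference in V1 to V3 change combines HIRREM with any effect of the request. The effect-size estimate that the Abstract offers as possible justification for larger trials would carry the same mixture.

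**Working it through.** **1. Does the request cover the HCC primary reading?** Count days from the last session.
- Request: from the first session to at least 6 × 7 = 42 days after the last.
- HCC V3 window: 4 × 7 = 28 to 6 × 7 = 42 days after the last.
- Since 42 ≤ 42, every in-window V3 reading is covered. V2 (days 1 to 14) is covered too. V4 (12 × 7 = 84 to 14 × 7 = 98 days) falls after the stated minimum.

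**2. Is there a CCC counterpart before V4?** The Overview, Number of HCC/CCC Sessions and Length of Study, Intervention Period and Post-Intervention Data Collection Visits sections tell CCC to continue current care and attend visits. None states an abstinence period. What the handout (Appendix B) or welcome email says is not shown.

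**3. Does the unqualified word participants settle it?** No. The plan also writes "Participants will receive 8-16 in-office intervention sessions over a maximum of 4 weeks", equally unqualified, and before V4 that can apply only to HCC.

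**4. Would a fixed number of days align the arms?** Count days from V1.
- Shortest HCC course: 8 sessions, two per day, take 4 days. With the first session on day 0, the last is on day 3. Earliest V3 = 0 + 3 + 28 = day 31.
- Latest HCC V3, taking the four-week maximum as 28 elapsed days: 14 + 28 + 42 = day 84.
- CCC V3: 8 × 7 = 56 to 10 × 7 = 70 days.

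The intervals are 31 to 84 days and 56 to 70 days, so a shared request should end at each participant's own V3.

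**5. Could an imbalance be seen?** For alcohol, probably. AUDIT-C is described under Alcohol Intake Screening and listed in Appendix A, and V3 is specified as "8-10 weeks after V1 for the CCC group, with all measures repeated". Read literally, that includes AUDIT-C. It is not among the listed secondary objectives, however, and Statistical Analysis names no use for it. No measure is described as recording recreational-drug use after V1.

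**6. Scale.** The documents give no blood-pressure effect of the request. Purely as an assumption, suppose 1 to 5 mmHg in those who change behaviour and a between-arm difference of 10 to 50 percentage points in that share. The shift is then 1 × 0.10 = 0.1 to 5 × 0.50 = 2.5 mmHg. For comparison, take the pilot standard errors of systolic change and assume that all 10 and all 18 participants contributed. The SDs are 5.5 × √10 = 17.4 and 1.91 × √18 = 8.1. With 10 per group, the standard error of a difference is SD × √(2/10), or 7.8 and 3.6 mmHg. These are supine recordings in other populations, so they are only a rough yardstick.

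**The case against.** The best reply is that no difference between the arms has been shown. The handout and/or welcome email goes to everyone scheduled for V1, before randomization, and may carry the request to both arms. Alcohol and drug use is already an exclusion in both arms, and the word anticipated looks forward into follow-up. AUDIT-C is repeated. Finally, this is an add-on trial with a wait-list control and no sham. HCC also receives 8 × 1.5 = 12 to 16 × 2 = 32 hours of sessions that CCC lacks, so the contrast is a package effect whatever is done about this request.

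Most of this stands as a limit on size and certainty. It does not remove the point. The plan issues the request on top of the exclusion, so it does not treat screening alone as sufficient. Session contact is inherent in delivering HIRREM, whereas the abstinence request can be separated from it and given to both arms.

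Three stronger readings are tempting, and the documents support none of them. A reader might infer that the primary contrast is biased; that cannot be said without knowing what CCC is told. A reader might count days under the request in each arm and treat the gap as the size of the problem. That measures how long a request lasts, not a difference in behaviour, and the CCC figure would only be the document's silence. A reader might see a proven contradiction, or a bias of known direction, in the therapy advice. The care to be continued is linked under Participants/Subjects to the provider's recommendation, so whether chiropractic, cranial-sacral or bio-energy work is included is unclear, and nothing shows which way suspension would act.

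**Conclusion.** The point holds in conditional form. As written, the alcohol and drug request covers the whole HCC V3 window and has no stated CCC counterpart before V4. If CCC does not receive it, the primary contrast estimates HIRREM plus the request, not the addition of acoustic stimulation alone.

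The size is unknown and may be small; if the exclusion is enforced in both arms, this part may be near zero. The illustrative range above lies below the rough standard error at 10 per group. This is therefore a minor-to-moderate matter of interpretation, worth raising because it is cheap to settle. The conclusion rests on the visible text, with the handout and welcome email unseen, and on the literal reading that AUDIT-C is among the measures repeated at V3.

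On the other therapies, the finding is only that the passages need reconciling.

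**What to change.** 1. State that the alcohol and drug request applies to both arms from V1 through each participant's own V3, in line with the exclusion already applied to both. Put it in both the handout and the welcome email, since Participants/Subjects allows either to be used.
2. Tabulate V3 AUDIT-C by arm beside the primary result.
3. If the sponsor prefers to keep the request for HCC only, describe the estimated effect, in the objective and the report, as HIRREM plus the accompanying request.
4. Reconcile the Abstract (Methods), Exclusion Criteria and Intervention Period text on chiropractic, cranial-sacral and bio-energy work, so that each arm's instruction is clear. This review takes no position on which instruction is right.
5. Optional: one short V3 item on alcohol, recreational-drug and listed-therapy use since V1. The protocol states no recall period for AUDIT-C, which in any case covers alcohol only.

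The cost is wording in three texts and one small table, plus one question if item 5 is adopted. The downside of item 1 is that the comparator becomes current care under the shared request, and must be described that way.
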